N-acetylcysteine (NAC) is generally well tolerated and has been extensively used at high doses in the treatment of acetaminophen overdose/toxicity for many years. The NAC dosage for acute acetaminophen overdose is a 140mg/kg loading dose, followed by a maintenance dose of 70mg/kg administered every 4 hours for 17 consecutive doses. The long-term use of NAC has also been investigated in six-month to three-year studies examining the efficacy and tolerability of NAC (dosed between 600-1200mg per day) in the treatment of chronic obstructive pulmonary disease COPD (Pela, Calcagni et al. 1999; Grandjean, Berthet et al. 2000; Stey, Steurer et al. 2000; Kasielski and Nowak 2001; Poole and Black 2001; Chikina, Iagmurov et al. 2002; Decramer, Rutten-van Molken et al. 2005). A recent study by Decramer and colleagues in 2005 concluded that there were no adverse events thought to be drug related in their study examining the use of 600mg/day of NAC in over 500 patients with COPD. Additionally, Chikina and colleagues found that the most effective dose of NAC in the treatment of COPD was 1200mg/day (the study examined doses of NAC ranging from 600-2400mg/day). A meta-analysis examining the efficacy of NAC in COPD, performed in 2000, revealed that NAC was well tolerated without significant adverse effects (Grandjean, Berthet et al. 2000). Although generally well-tolerated, the PDR indicates that adverse reactions reported with oral NAC include nausea, vomiting, diarrhea, headache (especially when used along with nitrates) and rashes. There are rare reports of renal stone formation. It is also important to note that rare reports of bronchoconstriction have occurred with intravenous NAC (but no reports of bronchospasm related to the oral use of NAC). Although there are no known contraindications to

NAC use, individuals with asthma will be excluded from the study given the rare, but potential, adverse effect of bronchospasm.

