In many cases subjects will be screened via telephone. The telephone screen will be used to inform the parent (primary caretaker) about the nature of the study, the duration of the study, number of visits, randomization, etc. The telephone screen will include collecting a brief history to exclude subjects that are unlikely to be eligible. People may not be eligible because of an ongoing medical problem (asthma or pregnancy), presence of an excluded psychiatric diagnosis (see exclusion criteria), or because they are unable to attend scheduled study visits. Interested subjects will be scheduled for a screening visit. The screening visit will occur over one visit. The overall purpose of the screening is to confirm that the subject meets all entry criteria. The first step in the screening visit will be to review the consent form, answer questions about the protocol and to obtain written informed consent. All procedures will be described to the subject in a developmentally appropriate manner.

2. **Inclusion/Exclusion Criteria:** What are the criteria used to determine subject inclusion or exclusion? How will eligibility be determined, and by whom?

Subjects will be well-characterized and must meet selection criteria to be enrolled. The measures used in the baseline assessment will be used by the principal investigators to determine if subjects meet inclusion/exclusion criteria.

Inclusion Criteria:

1. Children aged 8-17 years.
2. Primary diagnosis of OCD.
3. Duration of OCD greater than 6 months.
4. Significant Current OCD symptoms: Current CY-BOCS score greater than or equal to 16.

Exclusion Criteria:

1. Comorbid bipolar disorder, psychotic disorder, substance use disorder, developmental disorder or mental retardation (IQ<70).
2. Recent change (less than 4 weeks) in medications that have potential effects on OCD severity (such as Selective Serotonin Reuptake Inhibitors, clomipramine, naltrexone, lithium, psychostimulants, anxiolytics, or antipsychotics). Medication change is defined

to include either dose changes or medication discontinuation.

3. Asthma requiring medication use within the last 3 months (case reports have linked intravenous NAC administration with asthma exacerbation)
4. Known hypersensitivity or previous anaphylactoid reaction to acetylcysteine or any components in its preparation.
5. Positive pregnancy test or drug screening test.
6. Previous use of N-acetylcysteine (dose greater than 600mg for more than 2 weeks).

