throughout the trial (March, Karayal et al. 2007). Serious and unanticipated and related adverse events will be reported immediately to the HIC (using HIC form 6A), and any appropriate funding and regulatory agencies. Also, serious anticipated adverse events will be reported immediately to the HIC and others whenever their magnitude or frequency exceeds expectations. [name] will evaluate the adverse event and determine whether the adverse event affects the Risk/Benefit ratio of the study and whether modifications to the protocol (at Risks to Subjects) or consent form (at Risks and Inconveniences) are required.

Personnel responsible for the safety review and its frequency.

[name] will conduct a review of all adverse events at least quarterly and if any serious adverse events occur. He will evaluate the frequency and severity of the adverse events and determine if modifications to the protocol or consent forms are required. During the review process [name] will evaluate whether the study should continue unchanged, require modification, continue or close enrollment.

Since this is a study of a FDA-approved medication in children with OCD, we believe the risks involved in this study are greater than minimal risk to the child, but presenting the prospect of direct benefit to the individual subjects. However, assessment of adverse events, including grading of severity and attribution to research, will be conducted at each visit indicated below.

1. Attribution of Adverse Events

Clearly: The adverse event is clearly related to the intervention

Likely: The adverse event is likely related to the intervention

Possibly: The adverse event may be related to the intervention

Unlikely: It is unlikely that the adverse event is related to the intervention

Not: The adverse event is clearly not related to the intervention

2. Plan for Grading Adverse Events

The FDA's definition of serious adverse events (21 CFR 312)

SAEs include any untoward medical occurrence that at any dose results in death or the immediate risk of death, hospitalization or the prolonging of an existing hospitalization, persistent or significant disability/incapacity or congenital anomaly/birth defect (NOH Guide-6/11/99)

Grades of Risk:

0 = No Adverse Event or within normal limits

1 = Non-Serious Adverse Event

2 = Serious Adverse Event

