3. Plans for reporting serious and unanticipated and related adverse events, anticipated adverse events occurring at a greater frequency than expected, and other unanticipated problems involving risks to subjects or others to the HIC:

Serious and related unanticipated adverse events will be reported immediately to the HIC (using HIC form 6A), and any appropriate funding and regulatory agencies. Other unanticipated problems involving risks to subjects or others will also be reported to HIC.

Serious anticipated adverse events will be reported immediately to the HIC and others whenever their magnitude or frequency exceeds expectations. [name] will evaluate the adverse event and determine whether the adverse event affects the Risk/Benefit ratio of the study and whether modifications to the protocol (at Risks to Subjects) or consent form (at Risks and Inconveniences) are required. For the current study, the following individuals, funding, and/or regulatory agencies will be notified:

- a. All co-investigators

4. Plans for reviewing and reporting *non-serious anticipated and unanticipated* adverse events:

[name] will conduct a review of all adverse events at least quarterly. He will evaluate the frequency and severity of the adverse events and determine if modifications to the protocol or consent forms are required.

4. Confidentiality & Security of Data:

- a. What protected health information about subjects will be collected and used for the research?
- b. How will the research data be collected, recorded and stored?
- c. How will the digital data be stored? CD DVD Flash Drive Portable Hard Drive Secured Server Laptop Computer Desktop Computer Other
- d. What methods and procedures will be used to safeguard the confidentiality and security of the identifiable study data and the storage media indicated above during the subject participation in the study?
- e. What mechanisms are in place to ensure the proper use and continued protection of these data after the subject participation in the study has ceased?
- f. What will be done with the data when the research is completed? Are there plans to destroy the identifiable data? If yes, describe how, by whom and when identifiers will be destroyed. If no, describe how the data and/or identifiers will be secured.
- g. Who will have access to the protected health information? (such as the research sponsor, the investigator, the research staff, all research monitors, FDA, QUACS, SSC, etc.)

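### The serious adverse event definition has no important-medical-event criterion, so a non-life-threatening bronchospasm or anaphylactoid reaction treated without admission is graded non-serious and triggers no off-cycle review

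*Combined protocol and SAP*

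**What the plan says.** In Section IX, item 3, under the plan for grading adverse events, the definition opens "SAEs include any untoward medical occurrence that at any dose results in death or the immediate risk of death, hospitalization or the prolonging"; the last item there concerns a stay already under way. The definition closes with "persistent or significant disability/incapacity or congenital anomaly/birth defect (NOH Guide-6/11/99". Nothing follows that rests on medical judgement or on treatment given to avert one of these outcomes.

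The scale beneath it has three levels: 0 for no event, "1 = Non-Serious Adverse Event", and 2 for a serious event. There is no level between 1 and 2.

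The grade decides the route. The named reviewer "will conduct a review of all adverse events at least quarterly and if any serious adverse events occur". That review decides whether the study continues unchanged, is modified or closes enrolment. For non-serious events, anticipated or not, sub-item 4 of the same plan says only that the reviewer "will conduct a review of all adverse events at least quarterly".

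The protocol itself names the two hazards at issue. Background Information (Section VI, item 2) and Risks (Section IX, item 1) both say that "individuals with asthma will be excluded from the study given the rare, but potential, adverse effect of bronchospasm". Exclusion criterion 4 (Section VII) reads "Known hypersensitivity or previous anaphylactoid reaction to acetylcysteine or any components in its preparation".

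**The concern.** The trial adds NAC to existing treatment in children, and the protocol rates it as greater than minimal risk. The hazards it screens for at entry can be clinically important without causing admission or an immediate risk of death. If such an episode is treated and the child goes home, the plan's only severity label for it is the one that a mild headache would get.

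Two things are at stake. The first is timing: a serious grade is the only stated trigger for bringing the study-level risk-benefit review forward. The second is reporting: in a summary by grade, the event would sit among the non-serious ones.

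Group comparison will not make up for this. The Statistical Considerations concede limited power for infrequent events, and claim 80% power only for a side effect seen in one-third of NAC subjects and in none on placebo. A rare reaction has to be picked up by review of the single case, and the timing of that review depends on the grade.

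**Working it through.** The plan states no figure to reproduce. The check is a reading of the definition against one test case, followed by a comparison of intervals.

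**Test case:** a bronchospasm or anaphylactoid reaction, treated in an emergency department, without immediate risk of death and without admission.

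| Listed criterion | Met? |
|---|---|
| Death | No |
| Immediate risk of death | No, by construction |
| Hospitalization or its prolongation | No, child not admitted |
| Persistent or significant disability/incapacity | No |
| Congenital anomaly/birth defect | No |

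No criterion is met, so the event is Grade 1.

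**Routes open to a Grade 1 event**

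- Off-cycle study-level review: not triggered, because it requires a serious event.
- Immediate report to the HIC: not triggered. Both immediate routes (serious, unanticipated and related; or serious, anticipated and exceeding expected magnitude or frequency) require seriousness.
- Report as another unanticipated problem (sub-item 3): possible only if the event is judged unanticipated, and no time limit is stated.
- Study-level review at least quarterly (sub-item 4): applies.
- Assessment by the research team: applies at each visit (Safety Monitoring Plan), and when outside care is needed (Section X, item 4(e)).

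**Intervals**

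- Longest interval between reviews at the minimum frequency: 52 / 4 = 13 weeks, or 13 × 7 = 91 days.
- Blinded treatment: 12 weeks, or 12 × 7 = 84 days.
- An event in treatment week *t* that falls just after a review is next reviewed at about week *t* + 13. Since *t* + 13 > 12 for every *t* ≥ 0, that review can come after the child has finished blinded treatment.
- Visit gaps from the ratings table (baseline, weeks 2, 4, 8, 12): 2, 2, 4 and 4 weeks. The team would see the event within 4 weeks, or 28 days, even if the family did not report it sooner. This bound covers the blinded phase only; the 12 weeks of NAC offered afterwards to placebo subjects has clinical sessions as needed.

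**Does the entry screen remove the hazard?** Not on the text. Section VI, item 2 and Section IX, item 1 say that individuals with asthma are excluded. Exclusion criterion 3 excludes only asthma that required medication within the last 3 months. Under the criterion as listed, a child with asthma not recently medicated could enrol. These statements must be reconciled; the point about the definition stands either way.

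**The case against.** The strongest case on the other side is that little is left unattended.

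- **A life-threatening episode is already serious.** The definition includes immediate risk of death, with or without admission. This stands. A reader might infer that any bronchospasm treated without admission is graded non-serious; the text does not support that, and the gap is confined to non-life-threatening episodes.
- **The child does not wait a quarter.** Adverse events are graded and attributed at each visit, the research team first assesses events needing outside care, the clinician may adjust the dose at any time, and quarterly is a minimum. This also stands. A reader might infer that nobody looks at the event for up to 13 weeks; only the study-level review can wait that long. None of the earlier steps is stated to trigger that review.
- **The event might count as unanticipated and so reach the HIC.** Both risk sections say there are no reports of bronchospasm with oral NAC, and Section IX, item 1 mentions allergic reactions under unanticipated side effects. The classification is open to argument. But that route has no time limit, and sub-item 4 sends non-serious events to the quarterly review whether anticipated or not.
- **The definition may be wider than the list.** It is headed as the FDA's and uses the verb *include*, so it could be read as open-ended. A reader might go further and infer that the list departs from the cited regulation. The regulation's text is not in the documents, so neither reading can be settled from them. If raters could differ on whether the list is complete, that is a reason to state the criterion.

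**Conclusion.** The gap is real but narrow, and the point is minor. As written, a non-life-threatening bronchospasm or anaphylactoid reaction treated in an emergency department without admission is Grade 1, does not bring forward the study-level review, and is guaranteed only the at-least-quarterly one. At that minimum frequency the wait can be about 13 weeks against 12 weeks of treatment, while the research team would see the event within 4 weeks during the blinded phase.

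This assumes that the list is applied as a complete definition and that reviews run at the stated minimum.

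Two further inferences are not supported. The number of children who would start treatment during one review interval cannot be derived, because the stated project duration of 3-4 years includes follow-up and data analysis and is not an enrolment period. Nor would a serious grade by itself secure immediate reporting to the HIC: an anticipated serious event is reported immediately only when its magnitude or frequency exceeds expectations.

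**What to change.** In the plan for grading adverse events, extend the definition with a clause such as: *or an important medical event that required intervention to prevent one of these outcomes, including bronchospasm or anaphylactoid reaction needing urgent treatment, whether or not the child is admitted.* State that such events are Grade 2, so that the existing review on any serious adverse event applies to them.

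The cost is one sentence and an occasional extra off-cycle review by the existing reviewer. The change secures that review and the correct label in the results. It leaves the HIC reporting rules as they are.
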